The study is being conducted by the Pediatric Eye Disease Investigator Group (PEDIG) and is being coordinated by the Jaeb Center for Health Research in Tampa, Florida. The study is funded through a cooperative agreement from the National Eye Institute.

1.1 Objective

This study is designed to evaluate the effectiveness of increasing prescribed patching treatment from 2 to 6 daily hours after visual acuity has stabilized with initial treatment and amblyopia is still present. Children ages 3 to <8 years with visual acuity of 20/50 to 20/400 in the amblyopic eye will be enrolled in a run-in phase with 2 hours daily patching until no improvement, followed by randomization of eligible patients to patching 2 hours daily versus an average of 6 hours daily (42 hours per week). The primary objective is to determine if increasing patching dosage will improve visual acuity in patients with amblyopia still present after visual acuity has stabilized with initial treatment.

1.2 Rationale for the Study

Amblyopia is the most common cause of monocular visual impairment in both children and young and middle-aged adults. Both patching and atropine are accepted treatment modalities for the management of moderate amblyopia in children.¹ Many practitioners prescribe 2 hours daily patching as initial therapy for amblyopia. However, many children fail to achieve normal visual acuity in the amblyopic eye with this regimen. In a randomized trial conducted by PEDIG comparing patching regimens, 71 of 92 patients with moderate amblyopia (77%) had amblyopic eye visual acuity of 20/32 or worse after 4 months of patching 2 hours daily.² In another PEDIG randomized trial comparing patching to spectacles alone after a period of refractive adaptation, patients were treated with 2 hours daily patching and followed every 5 weeks until there was no improvement in amblyopic eye acuity. Fifty-five of 70 patients with moderate amblyopia (79%) and 14 of 14 patients with severe amblyopia (100%) had best-measured amblyopic eye visual acuity of 20/32 or worse after a median treatment period of 10 weeks.³ When improvement with initial therapy stops and amblyopia is still present, treatment options include increasing the dosage of current treatment, switching to another treatment, maintaining the same treatment and dosage for additional months, or combining treatments. Many clinicians will choose to increase the dosage of the current treatment, in part because families have become comfortable with that particular mode of treatment. However, it is unknown whether increasing occlusion dosage will improve amblyopic eye visual acuity in these patients. We are unaware of any reports of response to intensified treatment of amblyopia.

1.3 Synopsis of Study Design

The study consists of two phases:

- 1) A run-in phase during which all patients are treated with 2 hours of patching per day.
 - Patients may be enrolled either at the initiation of occlusion or during the course of treatment, provided that the prescribed treatment regimen to that point has been 2 hours of patching per day.
- 2) A randomized trial, beginning after visual acuity has stabilized and amblyopia is still present, in which the patient is randomized to either continue 2 hours of patching per day or increase patching time to an average of 6 hours per day (42 hours per week).

46 Major Eligibility Criteria for Run-in Phase (see section 2.2 for a complete listing)

- 47 • Age 3 to < 8 years
- 48 • Amblyopia associated with strabismus, anisometropia, or both
- 49 • Visual acuity in the amblyopic eye between 20/50 and 20/400 inclusive
- 50 • Visual acuity in the sound eye 20/32 or better and inter-eye acuity difference ≥ 3 logMAR lines
- 51 • Amblyopia treatment within the past 6 months subject to the following stipulations:
- 52 ➤ No more than 6 weeks of any amblyopia treatment other than spectacles (except for patients
- 53 being treated with 2 hours of patching per day who are entering the study on treatment)
- 54 ➤ No *simultaneous* treatment with patching and atropine
- 55 ➤ No use of atropine in combination with the sound eye spectacle lens reduced by more than
- 56 1.50 D
- 57 ➤ Maximum level of treatment within the past 6 months:
- 58 ▪ Patching: up to 2 hours daily
- 59 ▪ Atropine: up to once daily
- 60 • Wearing spectacles with optimal correction (if applicable); if amblyopic eye acuity is 20/80 or
- 61 better, then VA must be stable in glasses. If amblyopic eye acuity is 20/100 or worse, then
- 62 spectacles and patching can be initiated simultaneously.
- 63

64 Eligibility Criteria for Randomization:

- 65 • Amblyopic eye acuity of 20/40 to 20/160 with an inter-ocular difference of ≥ 2 lines, or amblyopic
- 66 eye acuity of 20/32 with 3 lines of IOD.
- 67 • Reasonable compliance with prescribed treatment, defined as wearing the patch at least 10 hours
- 68 per week.
- 69

70 Patching Run-In Phase

71 At enrollment, patients will begin (or continue, in circumstances described above) two hours daily

72 patching, and they will be followed every 6 weeks. Participation in this phase ends when there has

73 been no improvement of one or more lines in amblyopic eye acuity between 2 consecutive visits at

74 least 6 weeks apart, confirmed by a re-test, and patients have received at least 12 weeks of two hours

75 daily patching.

76

77 Randomized Treatment Groups

78 When there has been no improvement with two hours daily patching, eligible patients will be

79 randomized to one of two treatment regimens:

- 80 • Intensified treatment: 42 hours per week of patching (averaging 6 hours daily)
- 81 • Control: 2 hours daily patching
- 82

83 Sample Size

84 Seventy-nine patients will be randomized in each of the two treatment groups, for a total of 158

85 patients. This sample size has 90% power to detect a difference if the true difference in change from

86 baseline between groups is 0.075 logMAR at 10 weeks, with 2-sided type I error of 5%.

87

88 RCT Contact and Visit Schedule

- 89 • Phone call 5 weeks after randomization
- 90 • Primary outcome visit 10 weeks after randomization
- 91 • If amblyopic eye acuity improved by ≥ 1 line at primary outcome, follow-up visits at 10 week
- 92 intervals until no improvement of one or more lines, confirmed by a re-test

93

94 Primary Analysis

95 The primary outcome is amblyopic eye visual acuity 10 weeks after randomization.

[figure not shown]
96

97 The primary analytic approach for the amblyopic eye acuity will be a treatment group comparison of
98 the mean amblyopic eye acuity adjusted for baseline acuity using an analysis of covariance.

99

100 **1.4 Study Summary Flow Chart**

101

102

103

Chapter 2: Patient Enrollment

2.1 Eligibility Assessment and Informed Consent

A minimum of 158 patients are expected to be enrolled with a goal to enroll an appropriate representation of minorities. As the enrollment goal approaches, sites will be notified of the end date for recruitment. Patients who have signed an informed consent form can be randomized up until the end date, which means the minimum recruitment goal might be exceeded. The maximum number of randomized patients will be 178.

A patient is considered for the study after undergoing an eye examination by an investigator (as part of standard care) that identifies amblyopia meeting the eligibility criteria. As noted in subsequent sections, refractive error must be corrected with glasses if needed (as per standard care) before a patient can be enrolled into the trial.

For patients who appear eligible for the study following a “standard-care” examination, the study will be discussed with the child’s parent(s) or guardian. Parents or guardians who express an interest in the study will be given a brochure and a copy of the consent form. Written informed consent will be obtained from the parent or guardian prior to performing any study-specific procedures that are not part of the patient’s routine care.

2.2 Eligibility and Exclusion Criteria

The following criteria must be met for the patient to be enrolled in the study:

1. Age 3 to < 8 years
2. Amblyopia associated with strabismus (comitant or incomitant), anisometropia, or both
 - Criteria for strabismus: At least one of the following criteria must be met:
 - Heterotropia at distance and/or near fixation on examination (with or without spectacles)
 - History of strabismus surgery
 - Documented history of strabismus which is no longer present (which in the judgment of the investigator could have caused amblyopia)
 - Criteria for anisometropia: At least one of the following criteria must be met:
 - ≥ 0.50 D difference between eyes in spherical equivalent
 - ≥ 1.50 D difference between eyes in astigmatism in any meridian
3. Amblyopic eye has no myopia (≥ -0.25 D spherical equivalent).
4. Visual acuity, measured in each eye without cycloplegia within 7 days prior to enrollment using the ATS single-surround HOTV letter protocol as follows:
 - Visual acuity in the amblyopic eye between 20/50 and 20/400 inclusive
 - Visual acuity in the sound eye 20/32 or better
 - Inter-eye acuity difference ≥ 3 logMAR lines (i.e., amblyopic eye acuity at least 3 lines worse than sound eye acuity)
5. Amblyopia treatment within the past 6 months subject to the following stipulations:
 - No more than 6 weeks of any amblyopia treatment other than spectacles (except for patients being treated with 2 hours of patching per day who are entering the study on treatment)
 - No *simultaneous* treatment with patching and atropine

- 148 • No use of atropine in combination with the sound eye spectacle lens reduced by more than 1.50
149 D
- 150 • Maximum level of treatment within the last 6 months:
151 ➤ Patching: up to 2 hours daily
152 ➤ Atropine: up to once daily
- 153 6. Spectacle correction (if applicable) for measurement of enrollment visual acuity must meet the
154 following criteria and be based on a cycloplegic refraction that is no more than 6 months old:
- 155 a. Requirements for spectacle correction:
- 156 1) For patients meeting criteria for only strabismus (see 2.2 #2 above)
- 157 • Hypermetropia if corrected must not be undercorrected by more than +1.50 D
158 spherical equivalent, and the reduction in plus sphere must be symmetric in the two
159 eyes. Otherwise, spectacle correction is at investigator discretion.
- 160 2) For patients meeting criteria for anisometropia or combined-mechanism (see 2.2 #2 above)
- 161 • Spherical equivalent must be within 0.50 D of fully correcting the anisometropia
162 • Hypermetropia must not be undercorrected by more than +1.50 D spherical
163 equivalent, and reduction in plus must be symmetric in the two eyes
164 • Cylinder power in both eyes must be within 0.50 D of fully correcting the
165 astigmatism
166 • Cylinder axis in the spectacle lenses in both eyes must be within 6 degrees of the
167 axis of the cycloplegic refraction when cylinder power is ≥ 1.00 D
- 168 b. For patients with enrollment acuity of 20/80 or better, spectacles meeting above criteria must
169 be worn either:
- 170 1) for 16 weeks immediately prior to enrollment, or
- 171 2) until visual acuity in amblyopic eye is stable (defined as two consecutive visual acuity
172 measurements by the same testing method at least 4 weeks apart with no improvement of
173 one line or more)
- 174 • An acuity measurement done any of the following ways may be considered the first
175 of two consecutive measurements: 1) in current glasses, 2) in trial frames with full
176 correction of hypermetropia with cycloplegia, or 3) in new glasses. *Note: since this*
177 *determination is a pre-study procedure, the method of measuring visual acuity is not*
178 *mandated.*
- 179 c. For patients with enrollment acuity of 20/100 or worse, initiating treatment with spectacles and
180 occlusion simultaneously is allowed
- 181 7. No current vision therapy or orthoptics
- 182 8. No ocular cause for reduced visual acuity
- 183 • nystagmus per se does not exclude the patient if the above visual acuity criteria are met
- 184 9. Ocular examination within 6 months prior to enrollment
- 185 10. No prior intraocular or refractive surgery
- 186 11. No known skin reactions to patch or bandage adhesives
- 187 12. Parent willing to accept randomized treatment, has home phone (or access to phone), and willing to
188 be contacted by Jaeb Center staff
- 189 13. Parent does not anticipate relocation outside area of active study site
- 190

191 **2.3 Examination Procedures**

192 **2.3.1 Historical Information**

193 Historical information elicited will include the following: date of birth, gender, ethnicity, prior
194 amblyopia therapy (e.g., glasses, patching, pharmacologic, Bangerter filters), current spectacle
195 correction, and history of allergy to adhesive skin patches.
196

197 **2.3.2 Clinical Testing**

198 Examination procedures include:

199 1. Visual Acuity

- 200 • Measurement of visual acuity in each eye (right eye first) by the ATS single-surround HOTV
201 testing protocol.
202 • The ATS-HOTV visual acuity protocol must be used throughout the study. The protocol for
203 conducting the visual acuity testing is described in the ATS Testing Procedures Manual.
204 Aspects of the testing protocol that are specific to this study are:
205 ➤ Testing of the amblyopic eye must be done without cycloplegia (with spectacles, if worn)
206 no more than 7 days prior to enrollment.
207 ➤ Patients currently wearing spectacles must have enrollment acuity measured while wearing
208 spectacles - trial frames or phoropter cannot be used.

209 2. Ocular motility examination

- 210 • Measurement of alignment by Simultaneous Prism and Cover Test (SPCT) in primary position
211 at distance and near
212 • If performed within prior 7 days, it does not need to be repeated at time of enrollment

213 3. Ocular Examination

- 214 • Complete ocular examination, including dilated fundus examination, to rule out a cause for
215 reduced visual acuity other than amblyopia.
216 • If performed within prior 6 months, it does not need to be repeated at time of enrollment

217 4. Cycloplegic Refraction

- 218 • Cycloplegic refraction using cyclopentolate 1% as per investigator's usual routine
219 • If performed within prior 6 months, it does not need to be repeated at time of enrollment
220

Chapter 3: Patching Run-In Phase

3.1 Patching Run-In Phase Follow-up Visits

After enrollment, 2 hours of daily patching is prescribed. During the run-in phase, follow-up visits occur every 6 weeks as long as both of the following criteria are met:

- Amblyopic eye has improved at least one line from the previous visit
- Amblyopia is still present, defined as amblyopic eye acuity at least one line worse than the best sound eye acuity that has been recorded at any visit during the study

Note: If the amblyopic eye acuity meets the above criteria, follow-up will continue every 6 weeks even if the sound eye acuity has worsened from the prior visit.

At each follow-up visit, visual acuity will be tested in both eyes without cycloplegia and using the ATS HOTV visual acuity testing protocol with a study certified visual acuity tester. If the amblyopic eye acuity has not improved from the prior visit, acuity should be re-tested.

- If on the re-test there is still no improvement from the prior visit, and the prior visit was at least six weeks ago and the patient was on 2 hours of patching for at least 12 weeks, then the patient has completed the Patching Run-In Phase of the study; otherwise, the patient continues in follow-up.
- The better of the two amblyopic eye visual acuities at the last visit of the Patching Run-In Phase serves as the baseline amblyopic eye acuity for the Randomized Trial.

If a re-test is required and acuity improves on the re-test, then the re-test acuity serves as the value to which the next visit is compared when judging improvement.

Patients may be enrolled into the Patching Run-In Phase either at the initiation of occlusion or during the course of treatment, provided that the prescribed treatment regimen to that point has been 2 hours of patching per day.

3.2 Randomization After Completion of the Patching Run-In Phase

After patients complete the Patching Run-In Phase of the study, eligibility for randomization depends on amblyopic eye acuity, inter-ocular difference, and compliance with treatment.

Eligibility Criteria for Randomization:

- Amblyopic eye acuity of 20/40 to 20/160 with an inter-ocular difference of ≥ 2 lines, or amblyopic eye acuity of 20/32 with 3 lines of inter-ocular difference.
- Reasonable compliance with prescribed treatment, defined as wearing the patch at least 10 hours per week.

Children who do not meet the above criteria will end study participation.

3.3 Patients Who Skip the Patching Run-In Phase

Some patients will enter the randomized trial phase of the study without participating in the Patching Run-In Phase. These patients must have met the same applicable criteria for eligibility (see sections 2.2 and 3.2) and must have had no improvement in amblyopic eye visual acuity between 2 visits at least 6 weeks apart using the ATS HOTV protocol, confirmed by a re-test. These patients must be treated for at least 12 weeks with 2 hours daily patching by a study investigator.

265
266
267
268
269
270
271

For patients who skip the Patching Run-In Phase, visual acuity will be tested in each eye using the ATS HOTV visual acuity testing protocol using a study certified visual acuity tester. This testing (and re-testing to confirm no improvement) must be performed without cycloplegia and with the patient wearing spectacles if prescribed (i.e., trial frames cannot be used). The better of the two amblyopic eye visual acuities will serve as the baseline acuity for the Randomized Trial.

Chapter 4: Randomized Trial Phase

4.1 Randomized Treatment Groups

Each patient will be randomly assigned to one of two groups:

- Intensified treatment group: 42 hours per week of patching (averaging 6 hours daily), with spectacle correction (if needed)
- Control group: Continue 2 hours daily patching, with spectacle correction (if needed)

For both the intensified treatment group and the control group:

- Treatment is continued until there is no further improvement in amblyopic eye acuity (improvement defined as ≥ 1 line) between two consecutive 10-week visits, confirmed by a re-test. Once there is no improvement of one or more lines, the patient's participation in the study is over and treatment is at investigator discretion.

Notes

1. The study will provide patches.
2. If a patient is noncompliant with treatment, the parents should be encouraged to persist with their efforts to treat to the best of their ability.
3. Prior to deviating from the treatment protocols or prescribing non-protocol treatment, the situation should be discussed with the Protocol Chair.

4.2 Randomization of Eligible Patients

1. Once a patient is randomized, that patient will be included in the analysis regardless of whether the assigned treatment is received or not. Thus, the investigator must not randomize a patient until he/she is convinced that the parent/guardian will accept and comply with either of the treatment regimens. Regardless of whether the patient receives the assigned treatment or not, the patient is still considered enrolled in the study and every effort should be made to perform the follow-up examinations according to the study protocol.
2. The Jaeb Center will construct a Master Randomization List using a permuted block design stratified by site, which will specify the order of treatment group assignments. A patient is officially enrolled when the website randomization process is completed.

4.2.1 Delay in Randomization

1. Visual acuity testing and the ocular motility examination must be performed no more than 7 days prior to randomization. If randomization is delayed beyond 7 days, then these tests must be repeated to confirm eligibility and establish the baseline measures for the study.
2. No other parts of the examination (including the refraction) need to be repeated if they were performed within 6 months prior to randomization.

4.2.2 Compliance

A calendar log will be maintained by all families. These logs will be reviewed at each of the protocol visits. The investigator's assessment of compliance will be recorded on the Follow-up Examination Form.

317 **4.3 Follow-up Examinations**

318 All patients will have the following study visits / interactions after randomization:

- 319 • 5 weeks after randomization: telephone call
- 320 • 10 ± 1 weeks after randomization: primary outcome visit
- 321 • For patients whose amblyopic eye acuity has improved by ≥1 line at the 10-week primary
- 322 outcome visit, visits will occur every 10 ± 1 weeks until no improvement of one or more lines,
- 323 confirmed by a re-test, at which point study participation ends and treatment is at investigator
- 324 discretion.
- 325

Test	Visit / Interaction			
	Randomization	5 wk phone call	Primary Outcome 10 ± 1 wk	Every 10 ± 1 wks after primary outcome**
Telephone call		X		
Distance acuity each eye*	X		X	X
Ocular alignment	X		X	X
Titmus Fly	X		X	
Randot Preschool Test	X		X	

326 *Using ATS single-surround HOTV acuity testing protocol on study certified vision tester. The acuity testing at the
327 10-week primary outcome visit will be done by a masked examiner.

328 **For patients whose amblyopic eye acuity has improved by ≥1 at the 10-week primary outcome visit. Visits occur
329 every 10 ± 1 weeks until no improvement of one or more lines.

330
331 Additional visits can be performed at the discretion of the investigator. A Follow-up Examination
332 Form should be completed on the study website for every exam (not just the minimum required
333 exams).

334
335 **4.3.1 Telephone Call**

336 Each patient will be contacted by the coordinating center via telephone 5 weeks following
337 randomization to answer any questions and to encourage compliance with treatment.

338
339 **4.3.2 Primary Outcome Visit**

340 The primary outcome visit will occur 10 ± 1 weeks after randomization.

341
342 Testing will include the following:

- 343 1. Visual acuity
 - 344 • Measured in each eye (right eye first) by a certified masked examiner using the ATS single-
 - 345 surround HOTV acuity protocol on a study certified visual acuity tester
- 346 2. Titmus fly and Randot Preschool Stereoacuity test
- 347 3. Ocular alignment assessed with the SPCT
- 348 4. Re-testing of visual acuity in the amblyopic eye (if indicated)
 - 349 • If amblyopic eye visual acuity has not improved from randomization by at least one line,
 - 350 then it will be re-tested.
 - 351 • The results of the re-test will be used only to determine if the patient will continue study
 - 352 participation with the same study-mandated treatment. The first visual acuity will be used
 - 353 as the primary outcome visual acuity. If neither the test nor the re-test is one line better
 - 354 than the visual acuity at randomization, then study participation ends.
 - 355

356 **4.3.3 Follow-Up Visits after the Primary Outcome**

357 For patients in either treatment group with at least one line of improvement in amblyopic eye acuity at
358 the primary outcome examination, follow-up visits will occur every 10 ± 1 weeks until no
359 improvement of one or more lines is seen.

360
361 At each post-primary outcome visit, visual acuity will be measured in each eye (right eye first) by a
362 certified examiner using the ATS single-surround HOTV acuity protocol on a study certified visual
363 acuity tester. Acuity in the amblyopic eye will be re-tested if visual acuity has not improved from the
364 last visit by at least one line.

365
366 Study participation will end only after a post-primary outcome visit at which amblyopic eye acuity
367 shows no improvement of one or more lines on both an initial test and on a confirmatory re-test.
368

Chapter 5: Miscellaneous Considerations

369
370
371
372
373
374
375
376
377
378
379
380
381
382
383
384
385
386
387
388
389
390
391
392
393
394
395
396
397
398
399
400
401
402
403
404
405
406
407
408
409
410
411
412
413
414

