6.2 Secondary Efficacy Analyses

6.2.1 Visual Acuity Defined as a Binary Outcome

A secondary analysis will be a treatment group comparison of the proportion of patients who have improved by 2 or more logMAR visual acuity lines 10 weeks after randomization for each treatment group, adjusted for baseline acuity scores using logistic regression.

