6.2.3 Treatment Effect in Subgroups

The treatment effect in subgroups based on baseline factors will also be assessed in exploratory analyses. Interpretation of subgroup analyses will depend on whether the overall analysis demonstrates a significant treatment group difference. In the absence of an overall study difference, these subgroup analyses will be interpreted with caution.

507 The subgroups of interest are those based on visual acuity at the time of randomization, visual acuity at
508 the time of initial treatment, cause of amblyopia, length of prior treatment with 2 hours of patching,
509 and age at randomization.

510
511 In accordance with NIH guidelines, a subgroup analysis of treatment effect according to gender, as
512 well as race/ethnicity, will be conducted. However, based on results from previous ATS studies, a
513 treatment effect by these variables is not expected.

514
515 The general approach for these exploratory analyses will be to repeat the primary analysis within each
516 subgroup.

517 518 **6.2.4 Stereoacuity**

519 Differences between treatment groups in stereoacuity at the 10-week outcome will be assessed using a
520 comparison of the distributions with the exact Wilcoxon rank sum test.

521 522 **6.3 Primary Analysis for Safety**

523 **6.3.1 Sound Eye Acuity Data**

524 The loss of 2 or more lines in sound eye visual acuity from baseline to the 10-week masked exam will
525 be tabulated for each treatment group.

526 527 **6.3.2 Ocular Alignment**

528 Ocular alignment will be assessed at baseline and at 10 weeks after randomization. Development of
529 new strabismus (no tropia at baseline and the presence of near and/or distance tropia at follow-up) or
530 an increase from baseline ≥ 10 PD will be tabulated by treatment group. Similarly, disappearance of a
531 heterotropia and a decrease in the angle of a preexisting strabismus by ≥ 10 PD will be tabulated.

532 533 **6.4 Sample Size**

534 We are unaware of any previous literature on the response to treatment of amblyopia still present after
535 initial treatment. The sample size calculations were based on amblyopic eye visual acuity data in a
536 cohort of patients initially treated with 2 hours per day of patching from our previous ATS6 study.⁴ In
537 that study, patients were seen at 2, 5, 8, and 17 weeks after randomization. Based on improvement in
538 visual acuity between 8 and 17 weeks among patients defined as stable across the initial 2, 5, and 8

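### The week-10 masking requirement covers visual acuity only, so stereoacuity, a formally compared secondary efficacy outcome, may be measured by someone who knows the patching arm

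*Protocol*

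**What the plan says.** Section 4.3.2 lists the tests of the primary outcome visit one by one. Item 1, visual acuity, specifies who tests: "Measured in each eye (right eye first) by a certified masked examiner using the ATS single"-surround HOTV protocol. Item 2 reads in full "Titmus fly and Randot Preschool Stereoacuity test", and item 3 reads "Ocular alignment assessed with the SPCT". Neither names an examiner or mentions masking.

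The schedule table in section 4.3 agrees. The footnote that begins "The acuity testing at the" and continues "10-week primary outcome visit will be done by a masked examiner" is marked on the distance acuity row. The rows for ocular alignment, Titmus Fly and Randot Preschool carry no such mark.

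On the analysis side, section 6.2.4 stands under the heading "6.2 Secondary Efficacy Analyses" and states: "Differences between treatment groups in stereoacuity at the 10-week outcome will be assessed using a" comparison of distributions, by the exact Wilcoxon rank sum test. Section 6.3.2, under safety, says "Ocular alignment will be assessed at baseline and at 10 weeks after randomization" and then only tabulates new, increased, resolved or decreased deviations by group.

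**The concern.** Families and prescribers necessarily know whether 2 or 6 hours of patching was assigned. Under section 4.2.2 the patching calendars are looked at during protocol visits and the investigator's judgement of compliance is recorded, so staff at the week-10 visit are likely to know the arm. Protection against tester expectation then depends on who administers each test.

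Stereoacuity is read from the responses of children enrolled at 3 to under 8 years of age. It is reasonable to think that such a result can be influenced by the person giving the test. This is an inference from the type of test and the age range; the protocol does not say so. Acuity is also response-based, and the protocol masks it at the same visit. It gives no reason for treating stereoacuity differently.

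At stake is the interpretation of one secondary efficacy comparison. If testers at some sites knew the arm, a difference in stereoacuity could reflect treatment, tester expectation or both, and the data would not show which.

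**Working it through.** The point turns on wording, and the plan states no figure for stereoacuity that could be reproduced. The places are set side by side first; a hypothetical calculation follows.

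**Scope of masking at week 10**

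| Test | Section 4.3.2 | Schedule-table footnote | Use in analysis |
|---|---|---|---|
| Visual acuity | Masked examiner required | Masked examiner required | Primary (6.1); secondary binary outcome (6.2.1); sound-eye safety (6.3.1) |
| Titmus Fly, Randot Preschool | No examiner named | Not marked | Formal between-arm test (6.2.4) |
| SPCT alignment | No examiner named | Not marked | Tabulated only (6.3.2) |

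**Does any other text extend the masking?**

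- Section 6.3.1 refers to the week-10 examination as masked, but it is speaking of sound-eye acuity, which item 1 of 4.3.2 already covers.
- Section 6.3.2 (alignment) and section 6.2.4 (stereoacuity) refer to the 10-week time point without the word masked.
- Section 4.3.3, on visits after the primary outcome, asks for a certified examiner and does not ask for masking. The word is thus used selectively, and its absence from items 2 and 3 cannot be read as implied masking.
- The testing procedures manual is cited in section 2.3.2 for acuity testing only.

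No text requires masked stereo testing.

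**What a bias could do, on assumed values only**

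1. Children per arm with an outcome: 79 × 0.95 = 75.05, about 75 (79 per group in section 1.3; 5% loss in section 6.4).
2. Assumed, with no source in the documents: an ordinal stereo scale with an SD of 2 levels, and one extra level wrongly credited to a fraction p of one arm and to nobody in the other.
3. Mean shift in SD units = p × 1 / 2. For p = 10%, 20% and 30% this is 0.05, 0.10 and 0.15.
4. Noncentrality = shift × √(75/2) = shift × 6.12, giving 0.31, 0.61 and 0.92.
5. Two-sided 5% rejection of a true null, by normal approximation = Φ(noncentrality − 1.96) + Φ(−noncentrality − 1.96), giving about 6%, 9% and 15%.

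Step 5 approximates a comparison of means, whereas the plan uses an exact Wilcoxon test. The three rates follow correctly from the assumptions, but the assumptions are not evidence about this trial.

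**The case against.** The strongest reply is that this is silence and not an error. The protocol nowhere says that an unmasked person tests stereoacuity. A masked examiner has to be present at the visit, and the stereo tests are listed between the masked acuity test and the acuity re-test, so the same person may well do all of them. The procedures manual is not shown, so actual practice is unknown. Nor does the protocol name who reviews the calendars, and that the same person would test stereoacuity is conjecture. These points stand, and they limit the claim to what the protocol allows. They do not remove it: masking is assigned test by test, and who measures a formally compared outcome, masked or not, belongs in the protocol.

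Three stronger readings should be resisted.

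- A reader might infer that stereoacuity will be measured unmasked. The text permits this but does not state it.
- A reader might give alignment the same weight. Section 6.3.2 only tabulates it, under safety, with no formal comparison, and nothing shows that an examiner certified for acuity can perform SPCT.
- A reader might take the 6% to 15% rejection rates as an estimate of inflated type I error. They need over-crediting confined to one arm and an assumed SD. The documents support neither, nor any direction in which testers would lean.

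It is also fair to say that the consequence is bounded. Stereoacuity does not drive the sample size or the main conclusion, and the primary outcome is the first acuity test by the masked examiner.

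**Conclusion.** The point holds in limited form. The protocol's week-10 masking covers acuity only, and stereoacuity, which 6.2.4 tests formally between arms as a secondary efficacy outcome, may be measured by someone who knows the assignment. This rests on the wording of 4.3.2 and the table footnote, with no text elsewhere that widens the masking. It also rests on the inference that a young child's stereo result can be affected by the tester.

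The size of any bias cannot be determined from the documents. The masked primary outcome and the sample size are untouched. The change is worth making because it removes an avoidable doubt about a secondary endpoint at little cost.

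**What to change.** In section 4.3.2 and in the schedule-table footnote, state that the masked examiner who tests acuity at week 10 also administers Titmus Fly and Randot Preschool, before any discussion of treatment with the family.

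For SPCT alignment, record on the Follow-up Examination Form whether the examiner was masked. As alignment is only tabulated, that is enough.

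The cost is one sentence in each place, one form item, a few more minutes of the masked examiner's time and possibly brief instruction on the stereo tests for examiners who know only the acuity protocol. No visit is added, and the sample size and the planned analyses do not change.
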